8.1 Sample Size

Part 1: this study is exploratory. There is no hypothesis testing.

The sample size is based on the minimum number of subjects to reach a meaningful precision of the primary efficacy endpoint estimate (cure rate) in each arm, taking into account the stratification factor.

Taking into account the efficacy criteria for the selection of the dose (observed cure rate >70%), through simulations, Table 8 presents the probability of observing an overall cure rate $\ge 70\%$ based on different scenarios of true cure rates based on different strata, assuming a stratification of 40% moderate/heavy infections and 60% light infections. For example, a sample size of 50 evaluable subjects provides a probability of around 85% to observe a cure rate of $\ge 70\%$ if the overall true cure rate is 75% with 40% of moderate/heavy and 60% of light infections.

Probability of observ	Assumptions of Cure Rate in Light Infections						
cure rate \geq 70%, N=50,		70%	75%	80%	85%		
	50%	15%	27%	45%	64%		
Assumptions of Cure Rate in	55%	23%	38%	57%	76%		
Moderate/Heavy Infections	60%	33%	51%	70%	85%		
inicctions	65%	45%	63%	80%	92%		

Table 8. Probability of observing an overall cure rate ≥70% based on different scenarios of true cure rates based on different strata

Assuming an approximately 17% dropout rate, 60 subjects per arm will be randomized to ensure at least 50 evaluable subjects per arm.

Part 2: 30 subjects infected with *S. mansoni* aged 13 to 24 months (C8) and 10 subjects infected with *S. mansoni* aged 3 to 12 months (C9) will be included to evaluate tolerability and efficacy.

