8.5.1 General Considerations

Handling of subjects who drop out from the trial and missing data

For continuous endpoints, the imputation method of last observation carried forward will be used for the missing at the post-baseline measurement.

For binary endpoints, the imputation method of worst case will be used for the missing data at the post-baseline measurement.

The primary analysis will be based on mITT analysis population with missing imputations. All the observed cases will be analysed as sensitivity analysis.

Pharmacokinetic calculations

Not applicable..

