## 7 Sample Size/Randomisation

## 7.1 Sample Size

Part 1: this study is exploratory. There is no hypothesis testing.

The sample size is based on the minimum number of subjects to reach a meaningful precision of the primary efficacy endpoint estimate (cure rate) in each arm, considering the stratification factor.

There are limited historical data on the impact of the severity of infection on the observed cure rate. In the recent study by Keiser et al. (unpublished data), the observed cure rate in *S. mansoni* infected children varied between 55% and 60% in moderately infected children and 70% and 85% in light infected children depending on the dose. The table below presents the overall cure rate projections according to different assumptions of true cure rate in mild (low) and moderately infected children.

Overall cure rate (95%CI),	Assump	tions of Cure F	Rate in Light In	fections
(N=50)	70%	75%	80%	85%

	50%	62% (48%, 74%)	65% (52%, 78%)	68% (56%, 80%)	71% (60%, 82%)
Assumptions of	55%	64%	67%	70%	73%
Cure Rate in		(50%, 76%)	(54%, 80%)	(58%, 82%)	(62%, 84%)
Moderate/Heavy	60%	66%	69%	72%	75%
Infections		(52%, 78%)	(56%, 80%)	(60%, 84%)	(64%, 86%)
	65%	68% (54%, 80%)	71% (58%, 82%)	74% (62%, 86%)	77% (66%, 88%)

A minimum-clinical meaningful cure rate is considered as equal to 70%. With 50 evaluable patients enrolled, stratified as 40% moderate/heavy and 60% light, the corresponding 95% CI lower bound of an observed cure rate of 70% would be above ~58%, depending on potential difference between the strata. This sample size would also provide the minimum number of subjects to estimate the cure rate within strata.

Considering the efficacy criteria for the selection of the dose (observed cure rate >70%), through simulations, the table below presents the probability of observing an overall cure rate >= 70% based on different scenarios of true cure rates based on different strata, assuming a stratification of 40% moderate/heavy infections and 60% light infections.

Probability of observ	ring a	Assumptio	ns of Cure I	Rate in Ligh	t Infections
cure rate $\geq 70\%$ , N	=50,	70%	75%	80%	85%
	50%	15%	27%	45%	64%
Assumptions of Cure Rate in	55%	23%	38%	57%	76%
Moderate/Heavy Infections	60%	33%	51%	70%	85%
intections	65%	45%	63%	80%	92%

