#### Analysis set(s):

• Primary analyses will be based on the mITT and PP analysis sets.

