### **Overall clinical cure rate:**

Subjects cured of infection during the trial will be labelled as "responders". Responders will be defined as subjects with no parasite eggs (as determined by Kato-Katz method) in the End of Study

stool samples, 14-21 days after treatment, according to the eCRF page "Follow-up visit on D14-D21". Responders and non-responders will be coded as follows:

- For responders, *response* = 1
- For non-responders, response = 0

If the End of Study Kato-Katz egg count is missing, it will be imputed using the Last Observation Carried Forward (LOCF) approach. Subjects with missing data will be considered non-responders.

The proportion of responders in each cohort will be determined based on a binomial distribution. Exact 95% CIs will be calculated based on the Clopper-Pearson method. The PROC FREQ procedure in SAS will be used with the appropriate BINOMIAL and EXACT statements for point estimates and corresponding 95% CIs.

Point estimates and corresponding 95% CIs will be presented for cure rate, in terms of proportion of responders, by cohort. Response will be listed by cohort and subject. Estimates of cure rate will be presented graphically in the form of forest plots presenting means and 95% CIs.

Results will be presented for each analysis set.

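### The 85% chance of observing a cure rate of at least 70% assumes 50 evaluable children; under the primary mITT rule, with the planned 17% dropout counted as failures on 60, it is about 14%

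*Protocol*

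**What the plan says.** Protocol 8.1 states that "a sample size of 50 evaluable subjects provides a probability of around 85% to observe a cure rate of" at least 70% "if the overall true cure rate is 75% with 40% of moderate/heavy and 60% of light infections". The synopsis and SAP 7.1 repeat the figure. The randomised number is then set by allowing for loss: "Assuming an approximately 17% dropout rate, 60 subjects per arm will be randomized to ensure at least 50 evaluable subjects per arm". Sections 5.5.1 and 5.5.2 say that withdrawn subjects are not replaced.

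The analysis rules stand elsewhere:

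- Protocol 8.5.1: "The primary analysis will be based on mITT analysis population with missing imputations". Missing binary outcomes take the worst case, and the observed-case analysis is a sensitivity analysis.
- Protocol 8.4 and SAP 10.2: mITT is every randomised subject with a baseline measurement, less children who need malaria treatment. No post-baseline value is required.
- SAP 16.1.1, on cure: "Subjects with missing data will be considered non-responders".
- SAP 16.1.1, on analysis sets: "Primary analyses will be based on the mITT and PP analysis sets".

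The probability is tied to dose selection. SAP 7.1 introduces it with "Considering the efficacy criteria for the selection of the dose (observed cure rate >70"%), and Protocol 8.1 states the same criterion. In both documents the table that follows is computed for at least 70%.

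**The concern.** The planning probability and the primary analysis use different denominators. Table 8 counts cures among 50 children with an outcome. The primary analysis counts cures among up to 60, with every dropout scored as not cured. The sample-size section allows for dropout by randomising more children, but not for the effect of scoring those dropouts as failures.

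The 70% cure rate is the only efficacy criterion for dose selection stated in these documents, and the purpose of Part 1 is to choose the ODT dose for Part 2. If the criterion is applied to the protocol's primary analysis, an arm that truly cures 75% of children would usually fall short of it. If it is applied to PP, the same arm would usually reach it. With both sets labelled primary, neither document settles which result counts, and the trial is open label.

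**Working it through.** **Inputs**

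- Stratum mix 60% light and 40% moderate/heavy (Protocol 8.1): 30 and 20 of 50; 36 and 24 of 60.
- Cure rates for the 85% cell of Table 8: 85% light and 60% moderate/heavy. Overall 0.6 × 85% + 0.4 × 60% = 75%.
- 60 randomised, about 17% dropout, 50 evaluable. 10/60 = 1/6, and 50/(1 − 1/6) = 60.
- Missing outcome = not cured (Protocol 8.5.1, SAP 16.1.1). The SAP's carry-forward wording gives the same result, because every enrolled child is egg-positive at baseline.

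**Step 1: reproduce the plan's figure.** Let X = Bin(30, 0.85) + Bin(20, 0.60). The threshold is 0.70 × 50 = 35.

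- P(X ≥ 35) = 84.7%, against the stated 85%.
- All 16 cells of Table 8 reproduce to within one point in this way.

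**Step 2: the inequality.** 35/50 is exactly 70%, so a strict criterion needs 36 cures: P(X ≥ 36) = 75.6%. The table therefore uses at least 70%, although the criterion in the text is strict.

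**Step 3: apply the primary analysis rule.** The threshold is 0.70 × 60 = 42. With each child missing at random with probability d, the number of cures is Bin(36, 0.85(1 − d)) + Bin(24, 0.60(1 − d)). At d = 1/6 the stratum rates are 0.85 × 5/6 = 0.708 and 0.60 × 5/6 = 0.50, and the expected overall rate is 0.75 × 5/6 = 62.5%.

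| Dropout d | Expected mITT cure rate | P(≥ 42 of 60) | P(≥ 43 of 60), strict |
|---|---|---|---|
| 0% | 75.0% | 86.1% | 78.4% |
| 5% | 71.3% | 65.0% | 53.7% |
| 10% | 67.5% | 39.4% | 28.9% |
| 15% | 63.8% | 18.6% | 12.0% |
| 1/6 | 62.5% | 13.7% | 8.4% |
| 17% | 62.3% | 12.8% | 7.8% |
| 20% | 60.0% | 6.8% | 3.8% |

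If exactly 10 are missing rather than each child independently, 42 cures are needed among 50 evaluable children: P(X ≥ 42) = 8.2%. The 14% is thus the milder version.

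**Step 4: what would restore the claim.** With one sixth missing, the true rate among evaluable children must be 0.70/(5/6) = 84% merely for the expected estimate to equal 70%. It must be about 90% (single binomial) for an 85% chance of reaching it. Even the best cell of Table 8 (85% and 65%, stated 92%) falls to 20.7%.

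**Step 5: the two primary sets.** At planned dropout and a true 75%, the expected estimate is 62.5% in mITT and 75% among the evaluable children, taken here as the PP set.

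**The case against.** The strongest reply is that 14% is conditional. It requires the whole 17% to be missing outcomes that remain in mITT, and neither document defines evaluable or splits the 17%. Two kinds of non-evaluable child would not be mITT failures by default:

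- Children given malaria treatment leave mITT altogether. If 5 of the 10 were such children and 5 were missing, 39 of 55 would be needed, with a chance of 37.5%. If all 10 were, 84.7% returns.
- Some PP exclusions still have an observed outcome. With 5 missing and 5 observed but outside PP, 42 cures are needed from 55 observed children (33 light, 22 moderate/heavy), with a chance of about 48%.

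This widens the range but does not rescue the figure. The plan calls the 17% a dropout rate, and Protocol 5.5.2 says malaria-treated children are not withdrawn, so they are not dropouts in the plan's own terms. Even splits leave the chance far below 85%.

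It is also fair that 17% is an allowance rather than a forecast: treatment is a single supervised day with a short follow-up, and at 5% dropout the chance is 65%. That is still some 20 points below the stated value.

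Three further points have some force. The 85% is openly labelled as applying to evaluable subjects, and it is correctly computed; the fault is its mismatch with the analysis rule. The protocol says "this study is exploratory. There is no hypothesis testing", and the SMC weighs safety as well as efficacy under a charter not available here, so missing 70% on the point estimate need not decide the matter. And on the protocol's timetable Part 1 follow-up ended in December 2017, so a recomputed probability cannot change its size. None of these says which set is compared with 70%. The protocol alone would point to mITT, but the SAP adds PP as primary while stating in its section 9 that the protocol's methods were adopted.

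**Conclusion.** The concern holds. The stated 85% describes an observed-case or PP analysis of 50 children, not the protocol's primary analysis. Under mITT with missing counted as failure, the chance that an arm with a true 75% cure rate shows at least 70% is about 14% at the planned dropout.

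That figure assumes that all of the planned dropout is missing outcomes within mITT, that dropout is random and unrelated to cure, and the 60:40 mix with 85% and 60% stratum rates. The direction of the error does not depend on the exact dropout rate: any missing outcome scored as failure lowers the chance. The undefined analysis set and the inconsistent inequality are separate faults in the same criterion, and both need correcting.

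**What to change.** - **Protocol 8.1, synopsis and SAP 7.1:** state that the 85%, and Table 8 as a whole, apply to 50 children with an observed outcome. Beside it give the mITT figure with missing as failure: about 14% at 17% dropout, preferably with 39% at 10% and 65% at 5%. Say what the 17% is assumed to contain.
- **SAP 16.1.1:** name one analysis set and one missing-data rule as the result compared with 70%. Report the other set, and the observed-case analysis promised in Protocol 8.5.1, as sensitivity analyses.
- **Throughout:** use one inequality. If the strict form is kept, quote 75.6% instead of 85% for 50 evaluable children, and 8.4% instead of 13.7% for mITT.

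The cost is wording and a recomputed figure in two documents. The stated probability becomes less favourable. No patients, visits or assessments are added.

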8.2 Randomization

Part 1: Treatment allocation will be random and balanced at a ratio of 1:1:1:1:1.1. Randomization will be stratified by the infection severity (40% moderate/heavy and 60% light infections). After 20 subjects/arm are randomized, the SMC will decide on the inclusion of the 7^{th} arm.

Randomization will continue for arms C1-C6 at a ratio of 1:1:1:1:1:1 until a total of 40 subjects/arm are randomized.

If the C7 arm is included, randomization will continue with an allocation ratio of 1:1:1:1:1:3. If C7 arm is not included, the allocation ratio will remain the same (1:1:1:1:1).

Randomisation lists indicating a randomisation number and which treatment is to be given, will be produced prior to the start of the trial by the statistician at the PPD. Based on the randomisation lists sequentially numbered sealed envelopes which contain a randomisation number and the treatment allocation will be prepared. The sealed randomization envelopes will look identical and will be kept in a locked cupboard to which only the study pharmacist will have access.

Part 2: There is no randomization in this part.

8.3 Endpoints

8.3.1 Primary Endpoints

Clinical cure defined as no parasite eggs in the stools 14-21 days after treatment. Egg counts will be determined by Kato-Katz method. Cure rate will be calculated for each treatment arm as the percentage of subjects becoming egg-negative 14-21 days after treatment.

8.3.2 Secondary Endpoints

Egg Reduction Rate (ERR, %), calculated based on the arithmetic (and geometric) mean egg count per gram of stool (epg) before and 14-21 days after treatment as determined by Kato-Katz method

Cure defined as no parasite antigens in urine as assessed by the commercially available POC-CCA assay for *S. mansoni*

8.3.3 Other Endpoints

Changes in laboratory safety parameters and vital signs (body temperature, blood pressure and pulse rate)

Occurrence, nature, severity and outcome of adverse events

Occurrence of Adverse Drug Reactions per treatment group

8.4 Analysis sets

Part 1:

Modified intention-to-treat (mITT) population or analysis set includes all randomized subjects who have baseline measurement. Children who require malaria treatment after enrolment in the study will not be included in the mITT analysis set.

Per-protocol (PP) analysis set includes all subjects who are in the mITT population and have one post-baseline measurement without any clinically important protocol deviations. Details of the criteria for exclusion from the PP population will be provided in the SAP prior to first patient first dose.

Safety analysis set includes all subjects who have received at least one dose of treatment.

Part 2:

Modified intent-to-treat (mITT) population or analysis set includes all subjects (single arm, no randomization) who have baseline measurements. Children who require malaria treatment after enrolment in the study will not be included in the mITT analysis set.

Per-protocol (PP) analysis set includes all subjects who are in the mITT population and have at least one post-baseline measurement without any clinically important protocol deviation. Details of the criteria for exclusion from the PP population will be provided in the SAP prior to first patient first dose.

Safety analysis set includes all subjects who have received at least one dose of treatment.

8.5 Description of Statistical Analyses

All efficacy and safety endpoints will be analysed descriptively. Graphs will be produced as appropriate. Point estimation and 95% confidence interval (CI) will be calculated for primary and key secondary endpoints for each treatment arm.

Descriptive statistics for qualitative variables will include frequency counts and percentages. For proportion endpoints, the calculation of 95% CIs will be relied on the Clopper-Pearson (exact) method.

For continuous endpoints, the 95% CIs around the mean will be calculated where applicable. Descriptive statistics for quantitative variables will include: number of available observations, mean, median, lower quartile (Q1), upper quartile (Q3), minimum, maximum, and standard deviation.

8.5.1 General Considerations

Handling of subjects who drop out from the trial and missing data

For continuous endpoints, the imputation method of last observation carried forward will be used for the missing at the post-baseline measurement.

For binary endpoints, the imputation method of worst case will be used for the missing data at the post-baseline measurement.

The primary analysis will be based on mITT analysis population with missing imputations. All the observed cases will be analysed as sensitivity analysis.

Pharmacokinetic calculations

Not applicable..

8.5.2 Analysis of Primary Endpoints

Clinical cure rate (point estimation and 95% CI) will be calculated for each treatment arm on mITT and PP populations. 95% CI will be calculated on the Clopper-Pearson (exact) method. Subgroup analyses will be also conducted by severity of infections (stratification factor), gender and specific age groups.

8.5.3 Analysis of Secondary Endpoints

Egg reduction rate (ERR, %), calculated based on the arithmetic (and geometric) mean egg count per gram of stool (egp) will be calculated for each treatment arm after 14-21 days.

According to WHO guidelines, the group based egg reduction rates (ERR) after 14-21 days of PZQ drug administration is defined as:

ERR (%) = $100 \times (1\text{-arithmetic mean egg counts at post-baseline/arithmetic mean egg counts at baseline)$

To assess the corresponding ERRs for each treatment arm, Bootstrap resampling method with 10,000 replicates will be used to calculate 95% CIs for ERRs in each treatment arm.

Clinical cure rate assessed by POC-CCA assay for *S. mansoni* will be calculated (point estimation and 95% CIs) for each treatment arm.

8.5.4 Analysis of Safety and Other Endpoints

Values for all safety variables will be listed by subject and time point. Where appropriate, safety variables will be summarized using descriptive statistics.

Adverse events (AEs) will be coded by the Medical Dictionary for Regulatory Activities (MedDRA) preferred terms, and all summary tables for AEs will be organized by these categories. Frequency counts and percentages will be presented for subjects with at least 1 treatment emergent AE within each system organ class and preferred term, separated by treatment group. Treatment-emergent AEs will also be summarized by relationship to treatment and by severity within each treatment group.

By-patient listings of clinical laboratory data and vital signs will include indications of value that are outside the reference ranges, and values that are clinically significant. Tables describing out-of-reference range shifts will be provided for clinical laboratory test results and vital signs as appropriate and by treatment arm.

8.6 Interim and Additional Planned Analyses

The analyses will take part in a staggered manner for the different parts of the study, each part being self-contained.

A Safety Monitoring Committee (SMC) will be formed to evaluate the interim safety analysis, and will continue to monitor the safety data on a regular basis in both Part 1 and 2, including recommendations about additional monitoring measures that may be deemed necessary. The SMC will consist of internal Sponsor members and Coordinating Investigators. Details regarding SMC roles, responsibilities, activities, procedures to reduce potential bias and possible SMC recommendations will be provided in a separate SMC charter.

A safety (acute AE only) analysis is planned in Part 1 after 20 subjects from each of the treatment arms C1 to C6 are treated. The acute (24 hour) safety data of all six treatment arms will be summarized per each treatment arm by a Biostatistician, and evaluated by the Safety Monitoring Committee, to decide on the inclusion of the 7th arm (C7).

At the end of Part 1, the final analysis will be conducted on data as clean as possible. The Safety Monitoring Committee will assess the data (safety and efficacy) in order to recommend an optimal ODT dose (L-PZQ) or rac-PZQ) for Part 2.

Details will be outlined in the SMC charter and dose selection criteria described in a SAP prior to first subject first dose.

9 Ethical and Regulatory Aspects

This clinical trial will be conducted in compliance with the clinical trial protocol, ICH GCP, and any other applicable regulatory requirements.

9.1 Responsibilities of the Investigator

The Investigator is responsible for the conduct of the trial at the site and will ensure that the trial is performed in accordance with this protocol, the ethical principles outlined in the Declaration of Helsinki, ICH GCP, and any other applicable regulations. The Investigator must ensure that

only subjects whose parent/legal representative has given informed consent are included in the trial.

9.2 Subject Information and Informed Consent

An unconditional prerequisite for each subject prior to participation in the trial is written informed consent, which must be given before any trial-related activities are carried out. Adequate information must therefore be given to the subject by the Investigator or an appropriate designee (if local regulations permit) before informed consent is obtained.

Written informed consent will be provided by either one of the subject's parents or one of his/her legal representatives. In addition to the parental consent, children who are older than three and capable of assenting will provide oral assent. This will be recorded on the informed consent form.

A subject information sheet must be prepared in the local language, French, in accordance with ICH GCP and will be provided by the Sponsor for the purpose of obtaining informed consent/assent. In addition to providing this written information to a potential subject's parent or legal representative, the Investigator or a designate will inform them verbally of all pertinent aspects of the trial, using language chosen so that the information can be fully and readily understood by laypersons. The subject's parent or legal representative will be given sufficient time to read the information and the opportunity to ask questions and to request additional information and clarification.

If permitted by national regulations, a person other than the Investigator (designee) may inform the subject's parent or legal representative about the trial and sign the Informed Consent Form, as above.

If the subject's parent or his/her legal representative is illiterate, an impartial witness must be present during the information session. The witness will explain to the parent/legal representative the information contained in the written document and ask to give consent to have his/her child participating in the study. Consent of the subject's parent/legal representative will be confirmed by his/her fingerprint on the form whereas the witness will sign and date the form.

After the information is provided by the Investigator or an appropriate designee, the Informed Consent Form must be signed and dated by one of the subject's parents or his/her legal representatives and the Investigator or his designee.

The signed and dated declaration of informed consent will remain at the Investigator's site, and must be safely archived so that the forms can be retrieved at any time for monitoring, auditing and inspection purposes. A copy of the signed and dated information and Informed Consent Form should be provided to one of the subject's parents or his/her legal representatives prior to participation.

Whenever important new information becomes available that may be relevant to informed consent, the Investigator will revise the subject information sheet and any other written information to be provided to the subjects' parents or his/her legal representatives and submit

them to the IRB for review and opinion. Using the approved revised subject information sheet and other written information, the Investigator or an appropriate designee will explain the changes to the previous version to each trial subject' parent or his/her legal representative and obtain new written consent for continued participation in the trial. The subject' parent or his/her legal representative will be given sufficient time to read the information and the opportunity to ask questions and to request additional information and clarification about the changes.

